5.1.1 CTEP IND Agent(s): N/A

5.1.2 Other Agent(s): **INCB024360**

Combining INCB024360 with the multipeptide vaccine MELITAC 12.1 is a novel approach. Although no adverse findings in toxicology or safety pharmacology assessments have been described herein, and the most common grade 1 or 2 AEs at the recommended Phase-II dose (600 mg) include fatigue, nausea and vomiting, constipation, and anorexia; to decrease the possibility of unanticipated toxicities with the combination, the dose of INCB024360 in the first 3 patients treated in the study will be at the dose of 300 mg bid.

Weak cross-reactivity of INCB024360 to the human vasopressin 1a receptor, dopamine receptor, and carbonic anhydrase II may lead to changes in blood pressure or blood electrolytes. In 28-day toxicology studies, C_{max} values have exceeded the IC_{50} for the IDO1 enzyme (72 nM) by up to 37-fold and the IC_{50} for the vasopressin 1a receptor by up to 4-fold (13-fold in single-dose studies) in the absence of any toxicity, so the risk of unintended pharmacological activity is expected to be low.

5.1.3 Other Agent (s): **MELITAC 12.1**

MELITAC 12.1 vaccine comprises 100 μ g each of the 12 melanoma peptides plus 190 μ g tetanus toxoid peptide (Peptide-tet). Peptides are synthesized under good manufacturing practice (GMP) conditions by PolyPeptide Group (San Diego, CA; formerly Multiple Peptide Systems), reconstituted, mixed, sterile-filtered, and vailed under GMP conditions by Merck (Germany). The 12-melanoma peptide mixture and tetanus peptide preparation are made as separate sterile aqueous solutions to be administered in an emulsion with Montanide ISA-51 VG adjuvant (1 mL), using the 2-syringe method after emulsion stability and quality is verified. MELITAC 12.1 stimulated immune responses with an excellent safety profile and with presumptive evidence of efficacy in the adjuvant setting.

At this writing, the 12-MP has been administered in combination with Peptide-tet and GM-CSF in Montanide ISA-51 VG adjuvant to more than 200 participants enrolled in 3 studies run through the University of Virginia Human Immune Therapy Center (HITC) in collaboration with other centers (Mel39, Mel43, E1602) [[[name] 2007](#); [[name] 2009](#); [[name] 2010](#)] and 12-MP has been administered in Montanide ISA-51 VG adjuvant, with or without Peptide-tet in about 300 participants (Mel43, Mel44, E1602) [[[name] 2010](#); [[name] 2011](#); [[name] 2009](#)]. No data are available regarding the distribution and excretion of the vaccine preparation. In vitro studies have indicated the half-life of synthetic peptides in the presence of serum peptidases is short (approximately 22 seconds) [[Brinckerhoff 1999](#)]. However, in vivo data describing the metabolism of the vaccine are not available.

In the first 51 participants vaccinated with the 12-MP and Peptide-tet with GM-CSF in Montanide ISA-51 VG adjuvant, the majority of toxicities described have been of minimal severity. The most frequent AEs for participants receiving the 12-MP in

combination with Peptide-tet include maximum grade 1 fatigue (49%), maximum grade 1 chills (49%), maximum grade 1 headache (42%), and maximum grade 2 injection site reactions (69%). Other common AEs include maximum grade 1 sweating (27%), maximum grade 1 hyperglycemia (33%), maximum grade 1 myalgia (24%), and maximum grade 3 injection site reaction (27%). At this writing, at least 1 case of vitiligo and no cases of visual changes related to the vaccine after vaccination with the 12-MP and Peptide-tet administered with GM-CSF in Montanide ISA-51 VG adjuvant have been reported.

5.1.4 Other Modalities or Procedures: N/A

5.1.5 Investigational Imaging Agent Administration: N/A

5.2 **Definition of Dose-Limiting Toxicity:**

Dose-limiting toxicities (DLTs) include all Grade 3 AEs regardless of investigator attribution or relatedness except for those listed below.

Based on investigator determination the following Grade 3 toxicities can be deemed non-DLT:

- adverse event with a clear alternative explanation (e.g. due to disease progression)
- transient toxicities (≤ 72 hours)
- injection site reactions that are expected and do not require any surgical intervention or repair
- abnormal laboratory values without associated clinically significant signs or symptoms

There are two exceptions to the above. Grade 1 or greater ocular toxicities will be considered a DLT. Grade 2 LFT elevations will be considered a DLT.

In the event of a DLT, it will be determined by the safety team whether both the INCB024360 AND the MELITAC 12.1 will be permanently discontinued. In cases of vaccine injection site reaction or other vaccine related adverse events the INCB024360 may be continued if the vaccine related adverse event continues to show improvement. Management and dose modifications associated with the above adverse events are further outlined in [Section 6](#).

5.3 **General Concomitant Medication and Supportive Care Guidelines**

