Patients will receive 3 weeks of INCB024360, followed by continued INCB024360 plus 6 vaccinations with MELITAC 12.1. Patients who have disease progression while receiving anti-PD1 or anti-PDL-1 antibody treatment will be allowed to enroll and receive INCB024360 within 2-6 weeks of last antibody treatment administration. Patients enrolled within the 6 week window will be enrolled in Cohort B and administered INCB024360 orally at a dose of 100 mg twice daily continuously up to day 98 (3 months) plus vaccines. Patients who enroll in the study after confirmed disease progression on anti-PD1/PDL-1 after 6 weeks of receiving the last dose of antibody will be enrolled in Cohort A and receive 300 mg BID of INCB024360 plus vaccines.

Patients that show response at 3 months will be considered for additional INCB024360.

As a lead-in to ensure safety and tolerability of the combination of INCB024360 and MELITAC 12.1, the first 3 patients enrolled in the study will be at the dose of 300 mg bid staggering each patient's enrollment by at least 2 weeks so that the first patient will receive 2 doses of the vaccine in combination with INCB024360 before the second patient starts the combination of agents. Enrollment will be halted after the first 3 patients are enrolled to allow for observation of any toxicity before opening further enrollment. The next nine patients will receive either 300 mg bid of INCB024360 or 100 mg bid ([Table 5.1](#)). For patient safety, if a Dose Limiting Toxicity (DLT) occurs in the first three patients treated at the 300 mg BID dose level of INCB024360 + MELITAC 12.1 vaccine, the subsequent 9 patients will be treated with the dose of either 300 mg BID or 100 mg of INCB024360 + MELITAC 12.1. If two DLTs occur in the first 6 patients treated at the

300 mg dose of INCB024360 + MELITAC 12.1 the study will be stopped.

Treatment will be administered on an outpatient basis. Reported AEs and potential risks are described in [Section 7](#). Appropriate dose modifications are described in [Section 6](#). No investigational or commercial agents or therapies other than those described below may be administered with the intent to treat the patient's malignancy. The patient will be requested to maintain a medication diary of each dose of medication. The medication diary will be returned to clinic staff at the end of each course.

[Table 5.1. Agent Administration and Timing of Assessments](#)

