5.4 Duration of Therapy

Patients with surgically incurable stage III or IV melanoma and tissue amenable to serial biopsy will receive the sequential therapy with INCB024360 alone for 3 weeks followed

by continued INCB024360 plus 6 MELITAC 12.1 vaccines administered intradermally or subcutaneously on days 21, 28, 35, 56, 77, and 98 (weeks 3, 4, 5, 8, 11, and 14).

Serial biopsies will be obtained up to 14 days before starting INCB024360, on day 21 (before the first vaccine), and on day 42 (a week after the third vaccine). When feasible a biopsy will be obtained at week 16 (2 weeks after the sixth vaccination). If possible, tumors will be biopsied from patients coming off study, including for progression of disease.

In the absence of treatment delays due to AE(s), treatment may continue for up to 3 additional cycles of INCB024360 (a total of 4 cycles) after consultation with the trial Principal Investigator, CTEP, and the CITN, or until one of the following criteria applies:

- Disease progression by Response Evaluation Criteria In Solid Tumors (RECIST) or Immune-Related Response Criteria (irRC)
- Intercurrent illness that prevents further administration of treatment
- Unacceptable AE(s)
- Patient decides to withdraw from the study
- General or specific changes in the patient's condition rendering the patient unacceptable for further treatment in the judgment of the investigator

If additional cycles of INCB024360 are deemed appropriate for the patient, the INCB024360 will be given without the administration of the MELITAC 12.1 vaccines.

Only the end of treatment biopsy will be obtained if additional cycles of INCB024360 are approved for each patient.

In patients who are approved to receive additional cycles of INCB024360, a reduced volume of blood will be drawn for specific assays. ([Study Calendar, footnote ***](#))

A delay of up to 60 days between treatment cycles will be allowed.

In the event of unexpected serious AEs related to either component of the combination, treatment of the affected participant with INCB024360 and/or MELITAC 12.1 will be discontinued after analysis by the DSMC, Incyte, and CITN.

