5.5 Duration of Follow-up

Patients will be followed for 1 year after removal from study or until death, whichever occurs first. Patients removed from study for unacceptable AE(s) will be followed until resolution or stabilization of the AE. Unacceptable toxicity is defined as any of the following:

- 1) grade 3 or 4 adverse event requiring the patient to be removed from study treatment,
- 2) DLT's of grade 1 treatment related ocular toxicity, grade 2 allergic reactions,
- 3) >2 cm ulceration at the vaccination site or a vaccination adverse event requiring antibiotic treatment, debridement or narcotic management,

NOTE: Chronic inflammatory reactions at the vaccine sites are expected to occur in all participants who receive Montanide ISA-51. Induration may persist for days to months, but is not expected to require additional therapy. Sterile abscesses may occur in some participants. These are not a basis for discontinuation of the vaccines. However, if the inflammatory reactions develop significant ulceration of the skin (> 2 cm), then the patient would be taken off the study, however, this would not be considered a dose-limiting toxicity.

4) any unexpected grade 3 or greater non-hematologic or hematologic toxicity.

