6. DOSING DELAYS/DOSE MODIFICATIONS

All toxicity associated with prior treatment must resolve to grade 1 or less off steroid treatment for at least 2 weeks. Patients who have discontinued treatment for pulmonary, renal or neurologic toxicity or who have experienced grade 4 toxicity should not be enrolled in the study.

All related toxicities will be reviewed by the protocol P.I., participating site P.I.s, CTEP and the CITN Coordinating Center for an indication to change the dosing schedule.

The selected doses of INCB024360 and MELITAC 12.1 have been established as having excellent safety profiles. Dose escalation is not planned or necessary. However, when used together, unexpected toxicities might occur. Thus, rules for stopping will be incorporated in the event that dose-limiting AEs are observed.

Toxicities for each agent will be monitored continuously and will be graded by the NCI CTCAE v4.0 with stopping rules for AEs. At the discretion of the investigators, treatment may be held for up to 14 days to permit the evaluation or resolution of symptoms that may be unrelated to treatment but may affect patient safety (e.g., influenza, minor trauma).

DLT's include all Grade 3 AEs regardless of investigator attribution or relatedness except for expected grade 3 injection site reactions. ([section 5.5](#))

Based on investigator determination the following Grade 3 toxicities can be deemed non-DLT:

- adverse event with a clear alternative explanation (e.g. due to disease progression)
- transient toxicities (≤ 72 hours)
- injection site reactions that are expected and do not require any surgical intervention or repair

- abnormal laboratory values without associated clinically significant signs or symptoms

There are two exceptions to the above: Grade 1 or greater ocular toxicities will be considered a DLT. Grade 2 LFT elevations will be considered a DLT.

In the event of a DLT, it will be determined by the safety team whether both the INCB024360 AND the MELITAC 12.1 will be permanently discontinued.

Vitiligo will not be considered a DLT.

Pages 33, 34 and 35 include tables for some of the more common AE's including instructions for handling. For any AE's not listed in these tables, proceed in the following manner:
Grade 1 and Grade 2: Continue to monitor, follow and grade these adverse events.
Grade 3: Stop Protocol Therapy including both INCB024360 and MELITAC 12.1
Grade 4: Stop Protocol Therapy including both INCB024360 and MELITAC 12.1

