In addition, treatment will be discontinued for (a) Any DLT, (b) disease progression requiring other therapy, (c) noncompliance with study requirements, (d) other safety considerations in the judgment of the investigator, or (e) patient request.

The treatment regimen will be considered safe as long as the number of participants experiencing a treatment-related AE (DLT) does not exceed 33%. If more than 33% of patients accrued are known to have experienced a treatment-related DLT, the study will be closed to further accrual, except that 1 treatment related DLT observed out of the first 3 patients accrued will be acceptable and will not result in the closing of the study.

Nausea	Management/Next Dose for INCB024360	Management/Next Dose for MELITAC 12.1
≤ Grade 1	No change in dose	No change in dose
Grade 2	No change in dose	No change in dose
Grade 3	Off Protocol Therapy	Off Protocol Therapy
Grade 4	Off protocol therapy	Off protocol therapy
Recommended management: antiemetics		

Vomiting	Management/Next Dose for INCB024360	Management/Next Dose for MELITAC 12.1
≤ Grade 1	No change in dose	No change in dose
Grade 2	No change in dose	No change in dose
Grade 3	Off Protocol Therapy	Off Protocol Therapy
Grade 4	Off protocol therapy	Off protocol therapy
Recommended management: antiemetics		

Investigations (Liver Function Tests ALT + AST)	Management/Next Dose for INCB024360	Management/Next Dose for MELITAC 12.1
< Grade 1	No change in dose	No change in dose
Grade 1*	No change in dose	No change in dose

Investigations (Liver Function Tests ALT + AST)	Management/Next Dose for INCB024360	Management/Next Dose for MELITAC 12.1
Grade 2	Off Protocol Therapy	Off Protocol Therapy
Grade 3 or 4	Off Protocol Therapy	Off Protocol Therapy
*For Grade 1 LFT Elevations, increase LFT monitoring to twice weekly.		

Diarrhea	Management/Next Dose for INCB024360	Management/Next Dose for MELITAC 12.1
≤ Grade 1	No change in dose	No change in dose
Grade 2	No change in dose	No change in dose
Grade 3	Off Protocol Therapy	Off Protocol Therapy
Grade 4	Off protocol therapy	Off protocol therapy
Recommended management: physician discretion		

Neutropenia	Management/Next Dose for INCB024360	Management/Next Dose for MELITAC 12.1
≤ Grade 1	No change in dose	No change in dose
Grade 2	No change in dose	No change in dose
Grade 3	Off Protocol Therapy	Off Protocol Therapy
Grade 4	Off protocol therapy	Off protocol therapy
Recommended management: treatment of infection as appropriate		

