Thrombocytopenia	Management/Next Dose for INCB024360	Management/Next Dose for MELITAC 12.1
≤ Grade 1	No change in dose	No change in dose
Grade 2	No change in dose	No change in dose
Grade 3	Off protocol therapy	Off protocol therapy
Grade 4	Off protocol therapy	Off protocol therapy
Recommended management: platelet transfusions if indicated		

Fatigue	Management/Next Dose for INCB024360	Management/Next Dose for MELITAC 12.1
≤ Grade 1	No change in dose	No change in dose
Grade 2	No change in dose	No change in dose
Grade 3 or Grade 4	Off Protocol Therapy	Off Protocol Therapy
Recommended management: physician discretion		

Ocular Toxicity	Management/Next Dose for INCB024360	Management/Next Dose for MELITAC 12.1
≤ Grade 1	Off protocol therapy*	Off protocol therapy
Grade 2	Off protocol therapy	Off protocol therapy
Grade 3	Off protocol therapy	Off protocol therapy
Grade 4	Off protocol therapy	Off protocol therapy
*Defined as treatment-related grade 1 ocular toxicities		

Chills/fever/malaise following immunization	Management/Next Dose for INCB024360	Management/Next Dose for MELITAC 12.1
≤ Grade 1	No change in dose	No change in dose
Grade 2	No change in dose	No change in dose
Grade 3	Off protocol therapy if fails to resolve by the next scheduled immunization	Off protocol therapy if fails to resolve by the next scheduled immunization
Grade 4	Off protocol therapy	Off protocol therapy

Injection site reaction	Management/Next Dose for INCB024360	Management/Next Dose for MELITAC 12.1
≤ Grade 1	No change in dose	No change in dose
Grade 2	No change in dose	No change in dose
Grade 3	No change in dose*	No change in dose**
Grade 4	Off protocol therapy	Off protocol therapy

*See section 5.2

** MELITAC 12.1 vaccine may be given if the grade 3 injection site reaction combined area of skin ulceration is <2 cm

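### Sections 5.2, 5.5 and 6 do not agree on which events below Grade 3 are DLTs: Grade 2 allergic reactions, unrelated Grade 1 ocular events and Grade 2 LFT elevations

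*Combined protocol and SAP*

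**What the plan says.** **Section 5.2** makes Grade 3 events DLTs, lets the investigator exempt four kinds, and then adds events below Grade 3: "There are two exceptions to the above. Grade 1 or greater ocular toxicities will be considered a DLT". The second of the two is Grade 2 LFT elevation. Allergic reactions are not mentioned. After a DLT, the safety team decides on permanent discontinuation.

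**Section 5.5** opens a list with "Unacceptable toxicity is defined as any of the following". Item 2 of that list reads "DLT's of grade 1 treatment related ocular toxicity, grade 2 allergic reactions". The list follows directly on a sentence about patients removed for unacceptable AEs. Unacceptable AEs are a stopping criterion in 5.4, and 5.6 removes a patient when any 5.4 criterion applies.

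**Section 6** repeats the two low-grade DLTs of 5.2 and cites 5.5 in its DLT sentence. For events without a management table it says "Grade 1 and Grade 2: Continue to monitor, follow and grade these adverse events"; stopping starts at Grade 3. It then states "In addition, treatment will be discontinued for (a) Any DLT". Its ocular table takes Grade 1 patients off therapy, with the footnote "Defined as treatment-related grade 1 ocular toxicities".

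**Study-level rules.** Section 5.1: "If two DLTs occur in the first 6 patients treated at the" 300 mg dose, the study stops. Section 6 closes accrual if more than 33% of patients have a treatment-related DLT, with an allowance for one in the first three.

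**The concern.** Whether an event is a DLT should not depend on which section a site opens, and no section says which one prevails. For a Grade 2 allergic reaction the practical question is whether to give the remaining vaccinations, in an adjuvant for which Section 7.1.3 names a theoretical risk of anaphylaxis. For a Grade 1 ocular event judged unrelated, the question is whether the patient stays on treatment. Three or four sites are planned (13.3), so different sites could handle the same event differently.

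The same classification feeds the 5.1 stop. That rule needs only two DLTs among six patients, so the status of one event can decide it.

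**Working it through.** **1. The passages side by side**

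| Event | 5.2 | 5.5 | Section 6 text | Section 6 tables |
|---|---|---|---|---|
| Grade 2 allergic reaction | Not a DLT | DLT and unacceptable toxicity; treatment ends through 5.4 and 5.6 | Not a DLT; default is to continue and monitor | No table |
| Grade 1 ocular, related | DLT | DLT | DLT | Off therapy |
| Grade 1 ocular, unrelated | DLT (no attribution limit) | Not listed | DLT, so discontinue | Footnote excludes it |
| Grade 2 ocular | DLT | Not listed | DLT | Off therapy, no attribution limit |
| Grade 2 LFT elevation | DLT | Not listed | DLT | Off therapy |

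- *Allergic reaction:* 5.5 read with 5.4 stops treatment; the Section 6 default continues it.
- *Unrelated Grade 1 ocular event:* the stop-or-continue conflict lies inside Section 6, between its rule to discontinue for any DLT and its table footnote. Section 5.5 agrees with the footnote on classification but gives no instruction to continue.
- *Grade 2 LFT elevation:* 5.5 omits it, though Section 6 clearly takes the patient off therapy.

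**2. Which study-level rule each dispute reaches**

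- The 5.1 rule has no attribution limit, so both the allergic and the unrelated ocular dispute reach it.
- The 33% rule counts treatment-related DLTs only. An unrelated ocular event cannot reach it. A Grade 2 allergic reaction can, but only if it is treatment-related and the 5.5 list governs.

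**3. Size, as illustration only**

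The plan states no operating characteristic for these rules, so there is no figure to reproduce. The only counts in the documents are in Table 7.1.4.1: 51 patients on earlier vaccine regimens, attribution not stated. It shows 3/51 ocular events, all Grade 1, and 1/51 Grade 2 allergic rhinitis. It has no row for allergic reaction as such.

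Let *d* be the rate of disputed events. The chance of at least one in 12 patients is 1 − (1 − *d*)^12:

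- *d* = 0 (rhinitis does not count, all ocular events related): 0%
- *d* = 1/51 (rhinitis counts): 1 − (50/51)^12 = 21.2%
- *d* = 4/51 (rhinitis counts, all ocular events unrelated): 1 − (47/51)^12 = 62.5%

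For the 5.1 rule, let *b* be an assumed rate of undisputed DLTs, with independence. Then *p* = 1 − (1 − *b*)(1 − *d*), and the chance of two or more in six is 1 − (1 − *p*)^6 − 6*p*(1 − *p*)^5. For *b* = 10% and *d* = 1/51, *p* = 0.1176 and the result is 15.1%.

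| Assumed *b* | *d* = 0 | *d* = 1/51 | *d* = 4/51 |
|---|---|---|---|
| 5% | 3.3% | 5.9% | 16.5% |
| 10% | 11.4% | 15.1% | 27.3% |
| 20% | 34.5% | 38.3% | 49.6% |

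**The case against.** The best case against runs as follows.

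*Section 5.2 carries the DLT title; 5.5 concerns follow-up, and its list serves to say who is followed until an event resolves.* This has some force, but it does not settle the matter. Section 6 cites 5.5 in its DLT sentence, though beside injection-site reactions. Section 5.5 itself uses the term DLT, and elsewhere rules on DLT status when it says that ulceration over 2 cm is not one.

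*No patient need be re-vaccinated after an allergic reaction.* This stands. Section 6 lets the investigator stop for other safety reasons, all related toxicities are reviewed centrally, patients are observed for at least 20 minutes after each vaccination, and allergy to vaccine components is an exclusion. A reader might infer that the plan obliges sites to carry on vaccinating; it does not. These safeguards settle individual treatment decisions. They do not say whether the event counts toward the study stop.

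*Sections 5.2 and 6 do not stand together against 5.5 on ocular events.* This is right. A reader might infer a clean split between sections, with 5.5 telling sites to continue. The Section 6 footnote agrees with 5.5, and 5.5 says nothing about continuing. Nor does the phrase in 5.2 about counting events regardless of attribution extend to Grade 1 ocular events, since it is attached to Grade 3. The conflict rests only on the unqualified ocular wording.

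*The rates do not support a projection.* This also stands. The allergic figure is one case of rhinitis, the attribution of the ocular events is unknown, and the 51 patients are described in 5.1.3 as receiving GM-CSF, which this vaccine omits.

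**Conclusion.** The inconsistency is established from the text alone. The allergic-reaction conflict is direct: a DLT and stop in one place, not a DLT and continue in another. The ocular conflict is narrower, confined to Grade 1 events judged unrelated, and its opposing treatment instructions sit within Section 6. The missing LFT item in 5.5 is a gap in that list; the instruction itself is clear in Section 6.

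The consequence that does not depend on any rate is this: one disputed event plus one undisputed DLT among the first 6 patients at 300 mg either stops the study or does not. How often that would happen is unknown. A reader might take 62.5% as the chance of a dispute, or the right-hand column above as projected stopping probabilities. The documents do not support that: the figures depend on counting rhinitis as an allergic reaction, on the attribution of three ocular events, and on an assumed rate of other DLTs. The chance of a dispute runs from near 0 upward.

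This does not touch the primary endpoint. It should be corrected because it concerns patient safety and a study stop, and correcting it is cheap.

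**What to change.** Put one closed list in 5.2, and have 5.5 item 2 and Section 6 refer to it:

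*DLTs below Grade 3 are (a) treatment-related Grade 1 ocular toxicity; (b) Grade 2 ocular toxicity, regardless of attribution; (c) Grade 2 ALT/AST elevation; (d) Grade 2 allergic reaction.*

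Points to keep in the redraft:

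- The attribution limit belongs to Grade 1 ocular events only. Section 5.2 and the ocular table now act on Grade 2 ocular events whatever the cause, and that should not be loosened.
- Section 5.2 now counts every ocular event from Grade 1 upward. Say that the exemptions for Grade 3 events do not apply to ocular toxicity, so that a list headed *below Grade 3* does not open that door.
- If Grade 1 ocular events of any cause are meant to count, leave 5.2 unqualified and delete the relatedness wording from 5.5 and the ocular footnote instead.

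Add an allergic-reaction row to the Section 6 tables. At Grade 2 or higher, MELITAC 12.1 is off. INCB024360 is off unless the safety team judges the reaction vaccine-related and improving, which is the allowance 5.2 already makes.

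**Cost.** A text amendment, with no new visits, tests or reports. Counting Grade 2 allergic reactions makes an early stop slightly more likely, and the Grade 1 ocular rule relies on investigator attribution.

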2.3.1.3 Clinical Study (INCB024360-201)

INCB 24360-201 is a Phase Ib/II study of INCB024360 in combination with ipilimumab in subjects with advanced melanoma. Between April and August 2012, 8 subjects were enrolled in the Phase Ib portion of the study and were treated with INCB024360 300 mg bid (Cohort 1), 300 mg bid reduced to 100 mg bid (a continuation of Cohort 1 after hepatotoxicity was identified), or 100 mg bid (Cohort 2), each in combination with 3 mg/kg of intravenous (IV) ipilimumab every 3 weeks.

The initial 3 subjects treated with 300 mg bid of INCB024360 plus ipilimumab developed grade 3 or 4 elevations of aspartate aminotransferase/alanine aminotransferase (ALT/AST) on study days 76, 41, and 44, respectively. None of these subjects had elevated bilirubin, liver failure, or other evidence of severe liver injury. These subjects were discontinued from therapy and treated with IV methylprednisolone followed by oral prednisone on a tapering schedule until normal liver function recovered. At the time these elevations were reported, 4 additional subjects were already enrolled and receiving INCB024360 at 300 mg bid with 3 mg/kg IV of ipilimumab. All 4 of these subjects were evaluated and were found to have normal liver function tests (LFTs). Yet, in response to the LFT elevations in the first 3 subjects on study and after discussions with the US Food and Drug Administration (FDA), the dose of INCB024360 was reduced to 100 mg bid in these 4 subjects, and screening and enrollment continued to evaluate an initial dose of INCB024360 of 100 mg bid.

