10. STUDY CALENDAR

All baseline evaluations are to be conducted within 1 week before start of protocol therapy. Scans and x-rays must be done \leq 4 weeks before the start of therapy. In the event that the patient's condition is deteriorating, laboratory evaluations should be repeated within 48 hours before initiating the next cycle of therapy.

	Pre-Study -30 day	Pre-Study -7 day	Wk 0 Day 0	Wk 1 Day 7 +/- 2 d	Wk 2 Day 14 +/- 2d	Wk 3 Day 21 +/- 2d	Wk 4 Day 28 +/- 2d	Wk 5 Day 35 +/- 2d	Wk 6 Day 42 +/- 2d	Wk 8 Day 56 +/- 2d	Wk 11 Day 77 +/- 2d	Wk 14 Day 98 +/- 2d	Wk 16 Day 112 +/- 2d	Repeat ^b Cycles Wks ^c +/-2d	10 Wk Post-Tx F/U ^d F/U +/-14d	36 Wk Post-Tx FU F/U +/-30d	Off Study
INCB024360 daily			X	X	X	X	X	X	X	X	X	X	X	→	X		
MELITAC 12.1 vaccine**						X	X	X		X	X	X					
Informed consent	X																
Demographics	X																
Medical history	X																
Concomitant medication		X	X	X	X	X	X	X	X	X	X	X	X	X	X	X	X
Physical exam		X	X			X		X		X	X	X	X	X	X	X	X
Vital signs		X	X	X	X	X	X	X	X	X	X	X	X	X	X	X	X
Height		X													X		
Weight		X	X	X	X	X	X	X	X	X	X	X	X	X	X	X	X
Performance status		X	X	X	X	X	X	X	X	X	X	X	X	X	X	X	X
Tumor Biopsy ^{1,2*}			X ^a			X			X ³				X ³				X ¹
FNA ^{4,5}			X ^a			X			X				X ³				X ¹
CBC w/diff, plts (local lab)		X	X	X	X	X	X	X	X	X	X	X	X	X	X	X	X
Serum chemistry ⁶ (local lab)		X	X	X	X	X	X	X	X	X	X	X	X	X	X	X	X
B-HCG ⁷ (local lab)			X ⁷														
PBMC ⁵ and T-cell subsets			X			X			X			X	X ⁸				
IFN-gamma ELISpot***			X			X			X			X	X				
Confirmatory Tetramer staining			X			X			X			X					

	Pre-Study -30 day	Pre-Study -7 day	Wk 0 Day 0	Wk 1 Day 7 +/- 2 d	Wk 2 Day 14 +/- 2d	Wk 3 Day 21 +/- 2d	Wk 4 Day 28 +/- 2d	Wk 5 Day 35 +/- 2d	Wk 6 Day 42 +/- 2d	Wk 8 Day 56 +/- 2d	Wk 11 Day 77 +/- 2d	Wk 14 Day 98 +/- 2d	Wk 16 Day 112 +/- 2d	Repeat ^b Cycles Wks ^c +/-2d	10 Wk Post-Tx F/U [‡] F/U +/-14d	36 Wk Post-Tx FU F/U +/-30d	Off Study
Kyn/Trp ratio			X			X			X					X*			
RNA Cell Pellet for gene expression analysis			X			X			X					X			
Serum Cytokines			X			X			X					X			
INCB024360 level						X			X					X			
Circulating tumor cells			X											X			
PBMC storage***			X			X			X					X ⁸	X		
Serum storage			X			X			X					X ⁸			
EKG (pre-study and as indicated)	X																
Adverse event evaluation	X	X	X	X	X	X	X	X	X	X	X	X	X		X	X	X

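### The liver DLT definition in Sections 5.2 and 6 omits "or greater", so a symptom-free Grade 3 LFT rise can escape a count that a Grade 2 rise cannot (minor wording error)

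*Combined protocol and SAP*

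**What the plan says.** Section 5.2 makes Grade 3 adverse events dose-limiting whatever their attribution. It then lists Grade 3 toxicities that the investigator may deem non-DLT. One item on that list is "abnormal laboratory values without associated clinically significant signs or symptoms", with no carve-out for transaminases. Two exceptions follow, one ocular and one for the liver; the liver one reads "Grade 2 LFT elevations will be considered a DLT". Section 6 repeats the list and gives the exceptions as: "Grade 1 or greater ocular toxicities will be considered a DLT. Grade 2 LFT elevations will be considered a DLT". The ocular sentence is open upward; the liver sentence names one grade.

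Two numeric rules use the count:

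- Section 5.1: "If two DLTs occur in the first 6 patients treated at the" 300 mg dose, the study stops.
- Section 6: "If more than 33% of patients accrued are known to have experienced a treatment-related DLT", accrual closes. One such event among the first 3 patients is exempt.

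The LFT table in Section 6 takes the patient off both agents at Grade 2 and at Grade 3 or 4. Its footnote reads "For Grade 1 LFT Elevations, increase LFT monitoring to twice weekly". The Study Calendar (Section 10) schedules "Serum chemistry" weekly to day 42, then on days 56, 77, 98 and 112, each with a window of 2 days either way.

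**The concern.** A DLT definition should not get looser as the event gets worse. Here the Grade 2 event is mandatory, while the symptom-free Grade 3 event is left to the investigator, at 3 or 4 sites. The LFT table settles what happens to the patient; it does not say what is counted. The 33% rule also carries the plan's statement of when the regimen is regarded as safe, so a missed event would affect both stopping and the safety conclusion.

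Liver toxicity is a sensible place to want the count right. In study INCB024360-201 (Section 2.3.1.3), the first 3 patients on 300 mg bid with ipilimumab had Grade 3 or 4 transaminase elevations, and "None of these subjects had elevated bilirubin, liver failure, or other evidence of severe liver injury". A Grade 3 rise that fits the laboratory-value exclusion is therefore conceivable, though the section does not say whether these 3 patients had symptoms.

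**Working it through.** **Step 1. The text, grade by grade (Sections 5.2 and 6 read literally)**

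| LFT event | Counted as DLT? | Patient's treatment (Section 6 table) |
|---|---|---|
| Grade 2 | Yes, mandatory | Off both agents |
| Grade 3 with clinically significant signs or symptoms | Yes, unless another exclusion applies | Off both agents |
| Grade 3 without them | May be deemed non-DLT | Off both agents |

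Only the middle column of the last row is out of order.

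**Step 2. When the gap bites.** A patient with a recorded Grade 2 value counts anyway. So an event is lost only if all of these hold: no Grade 2 value is recorded on the way up or during recovery; there are no clinically significant signs or symptoms; and the investigator uses the discretion to exclude. The likeliest route is a first abnormal value already at Grade 3 after day 42, where draws are 56 − 42 = 14 or 77 − 56 = 21 days apart.

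**Step 3. Size.** The plan gives no DLT rate and no operating characteristics, so there is no figure to reproduce. Let p be the per-patient rate of LFT events that should count, and e the share deemed non-DLT. Both are assumptions. The counted rate is q = p(1 − e). Patients are taken as independent, all events as treatment-related, and no other DLTs occur.

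*Two in six:* P(stop) = 1 − (1 − q)^6 − 6q(1 − q)^5. For example, p = 0.33 and e = 0.10 give q = 0.297 and 1 − 0.121 − 0.306 = 0.573.

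| p | e = 0 | 5% | 10% | 25% | 50% |
|---|---|---|---|---|---|
| 20% | 0.345 | 0.320 | 0.296 | 0.224 | 0.114 |
| 33% | 0.642 | 0.609 | 0.573 | 0.460 | 0.259 |
| 50% | 0.891 | 0.865 | 0.836 | 0.726 | 0.466 |

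At p = 20% to 33% and e = 5% to 10%, the smallest loss is 0.345 − 0.320 = 0.025 and the largest 0.642 − 0.573 = 0.069.

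*33% rule, each outcome known before the next check.* An exact recursion over patients 1 to 12, with the first-3 exemption, triggers at 2 DLTs up to patient 6, 3 at patients 7 to 9, and 4 at patients 10 to 12.

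| p | e = 0 | 5% | 10% | 25% | 50% |
|---|---|---|---|---|---|
| 20% | 0.408 | 0.378 | 0.348 | 0.259 | 0.128 |
| 33% | 0.753 | 0.718 | 0.679 | 0.548 | 0.303 |

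The losses at 5% to 10% run from 0.408 − 0.378 = 0.030 to 0.753 − 0.679 = 0.074. If 33% is read as one third, p = 33% gives 0.673, 0.634 and 0.593 at e = 0, 5% and 10%, a loss of up to 0.080.

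*33% rule, late onset.* Section 13.3 expects about 3 patients a month. Assume starts on days 0, 14 and 56, then one patient every 10 days from day 91, with a check before each new patient through patient 11. A simulation gives:

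| Event known on | p | e = 0 | e = 10% | Loss |
|---|---|---|---|---|
| Day 49 | 20% | 0.125 | 0.102 | 0.023 |
| Day 49 | 33% | 0.328 | 0.269 | 0.059 |
| Day 77 | 20% | 0.040 | 0.032 | 0.008 |
| Day 77 | 33% | 0.108 | 0.088 | 0.020 |

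Events that surface late often arrive after most patients are enrolled, so there is less accrual left to protect.

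**The case against.** The strongest reply is that nobody would read the sentence literally. The protocol often writes a bare grade as a floor: its base rule names Grade 3 without adding higher grades, and Section 5.5 lists a Grade 1 ocular DLT without the words that Section 5.2 attaches to it. The liver sentence is also presented as an exception to the exclusion list, and an exception that left Grade 3 LFTs inside that list would restrict nothing. The LFT table stops both agents from Grade 2 upward. All of this stands as evidence of intent. It does not correct a definition that sites apply case by case.

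Other safeguards also stand. Enrollment pauses after 3 patients so that toxicity can be observed (Section 5.1), related toxicities get central review (Section 6), and Grade 1 brings closer monitoring. None changes what the numeric rules count.

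A reader might infer from the earlier study that silent Grade 3 rises are likely here and would fall between draws. The documents do not support that. Those cases arose with concurrent ipilimumab, which Section 3.2.2 bars within 8 weeks of enrollment. The first 3 occurred on study days 76, 41 and 44. Day 44 is inside this trial's day 42 window (days 40 to 44), and day 76 is one day before the day 77 draw and inside that window. The documents do not say how many of the 3 were Grade 3, whether they had symptoms, or whether a Grade 2 value came first. One of the 2 later cases was symptomatic with Grade 4 elevation. In study 101, none of the 7 melanoma patients had related Grade 3 or 4 LFT elevations.

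**Conclusion.** The wording error is real and appears in both sections; its severity is minor. It lets the worse liver event be left out of a count that must include the milder one, although the intention was almost certainly Grade 2 or greater.

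The practical effect is unknown and probably small: about 2 to 7 percentage points on the two-in-six stop, and about 3 to 8 on the 33% rule with outcomes known at once, for assumed rates of 20% to 33% and 5% to 10% excluded. With late onset and the assumed accrual pattern, the 33% rule loses about 1 to 6 points at 10% excluded. The large losses in the 25% and 50% columns would need a share of excluded events that the narrow conditions in Step 2 make hard to reach.

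Two stronger conclusions should not be drawn: that patients with Grade 3 rises would stay on treatment, or that the stopping rules are disabled. Section 6 contradicts the first, and the documents give no rate to support the second.

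**What to change.** In both sections, replace the liver sentence with: *Grade 2 or greater LFT elevations, whether or not symptomatic, are DLTs; the laboratory-value exclusion does not apply to them.* In the base rule of both sections, change Grade 3 to *Grade 3 or greater*. In the same edit, say whether the exclusions for events lasting 72 hours or less and for a clear alternative explanation may still be applied to LFTs, since they are open to Grade 3 rises in the same way.

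This is a protocol wording amendment, with no new visits, tests or patients. The downside is a slightly higher chance of an early stop for symptom-free transaminase rises, by the same differences shown in the working.
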